9.3. Risk-Benefit Rationale

Since the differences between the Reveal LINQ™ market-released device and the Reveal LINQ™ device with the LINQ investigational RAMware download are minimal, both devices are used in accordance with the Reveal LINQ™ implant manual and/or user manual, as applicable. The risks associated with the device are similar as would be the case if the subject received a Reveal LINQ™ device outside the study context. The risks introduced by the LINQ HF investigational RAMware are being evaluated and risk control measures being implemented to reduce the risk to as low as possible to minimize subject harm.

The study requirements for careful physician selection and training carry potential benefits that may be present if the subject was not enrolled in the study. Hence, for individual subjects, participation in the study may have greater benefit than risk. Moreover, the value of the knowledge to be gained by conducting this clinical study could help in the diagnosis of future patients. Lastly, the prospective benefit to subjects of having Reveal LINQ™ cardiac monitoring, with the potential to diagnose life-threatening arrhythmias, may provide the subject with clinical benefit.

10. Adverse Event Assessments

10.1. Definitions/Classifications

Reveal LINQ™ system and procedure-related adverse events will be collected throughout the study duration, starting at the time of signing the Patient Informed Consent Form. In addition, all serious adverse events (SAEs) leading to death should be reported, regardless of relatedness.

Reporting of these events to Medtronic will occur on an AE Form, including date of AE, treatment, resolution, assessment of both the seriousness of the AE and the relatedness to the device or procedure. Each AE must be recorded on a separate AE eCRF. Documented pre-existing conditions are not considered AEs unless the nature or severity of the condition has worsened. Unavoidable AEs, listed in Table 6, need not be reported unless the AE worsens or is present outside the stated timeframe post-insertion.

For AEs that require immediate reporting (see Table 6), initial reporting may be done by contacting the study sponsor per the sponsor contact information. The original completed AE CRF must be submitted to Medtronic as soon as possible.

Any medication, whether cardiovascular or not, associated with the treatment of an AE must be reported. Medication changes that are not related to adverse events will not be collected.

Subject deaths are also required to be reported. Refer to Section 11.4 for Subject Death collection and reporting requirements.

10.1.1. Device Deficiencies

Device deficiency (DD) information will be collected throughout the study and reported to Medtronic. Note that DDs that result in an Adverse Device Effect (ADE) to the subject should be captured as an AE CRF only.

10.1.2. Event Updates and Resolution

For any changes in status of a previously reported AE (i.e. change in actions taken, change in outcome, change in relatedness), information needs to be updated on, or added to the original AE

form. All AEs must be followed until the AE has been resolved, the subject dies or exits the study, or until study closure, whichever occurs first.

At the time of study exit, all collected AEs with an outcome of "Unresolved" must be reviewed and an update to the original AE must be reported. At a minimum, if there are no changes to the description, relatedness, test and procedures or actions taken, the outcome must be updated to reflect "Unresolved at time of study exit".

10.2. Definitions/Classifications

Where the definition indicates "device", it refers to any device used in the study. This might be the device under investigation, or any market released component of the system, and includes but is not restricted to: the Reveal LINQ™, the programmer, and insertion tools.

Table 6: Adverse Event and Device Deficiency Definitions

General	
Adverse Event (AE)	
Any untoward medical occurrence, unintended disease or injury, or untoward clinical signs (including abnormal laboratory findings) in subjects, users or other persons, whether or not related to the investigational medical device
 
NOTE 1: This definition includes events related to the investigational medical device or the comparator. NOTE 2: This definition includes events related to the procedures involved.

Adverse Device Effect (ADE)	
Adverse event related to the use of an investigational medical device
 
NOTE 1: This definition includes adverse events resulting from insufficient or inadequate instructions for use, deployment, implantation, installation, or operation, or any malfunction of the investigational medical device. NOTE 2: This definition includes any event resulting from an error use or from intentional misuse of the investigational medical device.

Device Deficiency (DD)	
Inadequacy of a medical device with respect to its identity, quality, durability, reliability, safety or performance.
 
NOTE 1: Device deficiencies include malfunctions, use errors and inadequate labeling.

Relatedness	
Procedure Related	
An Adverse Event that is directly related to the insertion or surgical modification of the system.
 
NOTE: In general, this excludes events that are inherent to any surgical procedure (e.g. anesthesia complications) as well as indirect subsequent consequences of the procedure (e.g. reaction to pain medication).

Reveal LINQ System Related (includes all implantable components and features, associated introduction tools, operational and installed software and programmers as defined in the Clinical Investigation Plan)	An adverse event that results from the presence or performance of any component of the system. Device-related : An adverse event that results from the presence or performance (intended or otherwise) of the device. RAMware-related : An adverse event that results from the presence or performance (intended or otherwise) of the RAMware. Programmer Related : An adverse event that results from the presence or performance (intended or otherwise) of the programmer Insertion Tool Related : An adverse event that results from the presence or performance (intended or otherwise) of the insertion tool. Holter Related : An adverse event that results from the presence or performance (intended or otherwise) of the implant tool.
Cardiovascular Related	An Adverse Event relating to the heart and the blood vessels or the circulation (e.g. Atrial Fibrillation, Myocardial Infarction, stroke, perivascular disease)

Not Related	
Relationship to the device or procedures can be excluded when:
 
▪ The event is not a known side effect of the product category the device belongs to or of similar devices and procedures;▪ The event has no temporal relationship with the use of the device or the procedures;▪ The serious event does not follow a known response pattern to the medical device (if the response pattern is previously known) and is biologically implausible;▪ The discontinuation of medical device application or the reduction of the level of activation/exposure – when clinically feasible – and reintroduction of its use (or increase of the level of activation/exposure) do not impact the serious event;▪ The event involves a body-site or an organ not expected to be affected by the device or procedure;▪ The serious event can be attributed to another cause (e.g., an underlying or concurrent illness/clinical condition, an effect of another device, drug, treatment, or other risk factors);▪ The event does not depend on a false result given by the device used for diagnosis (when applicable);▪ Harms to the subject are not clearly due to use error;▪ In order to establish the non-relatedness, not all the criteria listed above might be met at the same time, depending on the type of device/procedures and the event.
Unlikely	The relationship with the use of the device seems not relevant and/or the event can be reasonably explained by another cause, but additional information may be obtained.
Possible	The relationship with the use of the investigational device is weak but cannot be ruled out completely. Alternative causes are also possible (e.g. an underlying or concurrent illness/clinical condition or/and an effect of another device, drug or treatment). Cases were relatedness cannot be assessed or no information has been obtained should also be classified as possible.
Probable	The relationship with the use of the investigational device seems relevant and/or the event cannot reasonably explained by another cause, but additional information may be obtained.

Causal Relationship	
The event is associated with the device or study procedures beyond reasonable doubt when:
 
▪ The event is a known side effect of the product category the device belongs to or of similar devices and procedures;▪ The event has a temporal relationship with device use/application or procedures;▪ The event involves a body-site or organ that the device or procedures are applied to or the device or procedures have an effect on;▪ The serious event follows a known response pattern to the medical device (if the response pattern is previously known);▪ The discontinuation of medical device application (or reduction of the level of activation/exposure) and reintroduction of its use (or increase of the level of activation/exposure) impact on the serious event (when clinically feasible);▪ Other possible causes (e.g., an underlying or concurrent illness/clinical condition or/and an effect of another device, drug, or treatment) have been adequately ruled out;▪ Harm to the subject is due to error in use;▪ The event depends on a false result given by the device used for diagnosis (when applicable);▪ In order to establish the relatedness, not all the criteria listed above might be met at the same time, depending on the type of device/procedures and the serious event.
Seriousness	

Serious Adverse Event (SAE)	
Adverse event that
 
a) led to death, b) led to serious deterioration in the health of the subject, that either resulted in
 
 1) a life-threatening illness or injury, or 2) a permanent impairment of a body structure or a body function, or 3) in-patient or prolonged hospitalization, or 4) medical or surgical intervention to prevent life-threatening illness or injury or permanent impairment to a body structure or a body function, 
c) led to fetal distress, fetal death or a congenital abnormality or birth defect
 
NOTE 1: Planned hospitalization for a pre-existing condition, or a procedure required by the CIP, without serious deterioration in health, is not considered a serious adverse event. (ISO 14155:2011, 3.37)

Serious Adverse Device Effect (SADE)	
Adverse device effect that has resulted in any of the consequences characteristic of a serious adverse event. (ISO 14155:2011, 3.36)

Other	
Unanticipated Adverse Device Effect (UADE)	
Any serious adverse effect on health or safety or any life-threatening problem or death caused by, or associated with, a device, if that effect, problem, or death, was not previously identified in a nature, severity, or degree of incidence in the investigational plan or application (including a supplementary plan or application), or any other unanticipated serious problem associated with a device that relates to the rights, safety, or welfare of subjects. (21 CFR 812.3(s))

Acute Decompensated Heart Failure (ADHF) Event	
Any cardiovascular-related (including hypervolemia) Health Care Utilizations (HCUs) for any one of the following events.
 
 • Admission with primary diagnosis of HF • Intravenous HF therapy (e.g. IV diuretics/vasodilators) or ultrafiltration at • any one of the following settings: • Admission with secondary/tertiary diagnosis of HF • Emergency Department • Ambulance • Observation Unit • Urgent Care • HF/Cardiology Clinic

Unavoidable Adverse Event	An Adverse Event inherent to a surgical procedure that is expected to occur in all subjects for a projected duration according to the Investigator's opinion, including, but not limited to:	
Event Description		Timeframe (hours) from the Surgical Procedure
Pocket site / Incisional pain		72
Mild to moderate bruising / ecchymosis		168

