8.5.3. Right Heart Catheterization Procedure

A two-month blanking period post-insertion to allow for pocket maturation would be preferred prior to the first right heart catheterization (RHC) procedure.

Prior to each RHC procedure, Holter mode will be enabled on the LINQ device using a 2090 programmer with investigational software, and a DR220 Holter Recorder will be applied to the subject to collect high-resolution impedance and ECG. See Appendix C for more information on applying the Holter.

The RHC will be performed according to the participating institution's procedure. There are no study-related requirements around the performance or timing of the procedures, other than measures to collect comprehensive data and assure quality. A standardized procedure will be followed to ensure appropriate placement of the pressure transducer. The location of the pressure transducer will be measured from the substernal notch down and recorded at the first procedure. This measurement will be used to ensure consistent placement of the pressure transducer at subsequent procedures. Both the proximal and distal ports of the Swan-Ganz catheter will be connected for continuous recording of right atrial and pulmonary artery pressures. Cardiac output and systemic blood pressure will be measured frequently throughout the procedure and at least every 2 minutes during the drug or exercise challenge and recovery. ECG and hemodynamic waveform data will be recorded on the lab recording system, a copy of which will be provided to Medtronic. Lab and Holter data will be synchronized by introduction of noise on the ECG signal which will be common to both systems (e.g., briefly disconnecting or tapping on an electrode).

As part of the standard procedure, subjects may be administered an acute drug or exercise challenge. Alternatively, subjects with an implanted PA pressure monitor may undergo a right heart catheterization procedure without any associated drug or exercise challenge. The Holter will continue to record data throughout the recovery/observation period with the subject remaining supine or with moderate head elevation if necessary. The timing and description of any positional changes will be noted in the CRFs. At the conclusion of the recovery period, the posture test will be performed, the Holter recorder will be removed, and Holter mode will be disabled (see Appendix C for more information).

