8.5.8. Posture Test

A posture test will be conducted at each right heart catheterization procedure, and at 6 Month and 12 Month scheduled visits in subjects with implanted PAP sensors. Subjects will be requested to be put in four different postures: standing, supine on back, lying down on left side and lying down on right side. During each posture, the Medtronic 2090 Programmer with the LINQ HF investigational RAMware will be used to store the x, y, and z-axis accelerometer values to calibrate the posture measurements. Refer to Appendix C for more details.

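### Because 'Procedure Related' covers only insertion or surgical modification, non-fatal adverse events from other study procedures, such as the posture test, need not be reported as AEs

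*Combined protocol and SAP*

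**What the plan says.** Section 10.1 sets the collection rule: Reveal LINQ "system and procedure-related adverse events will be collected throughout the study duration", starting at consent. It adds one exception, that "all serious adverse events (SAEs) leading to death should be reported, regardless of relatedness".

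Table 6 in Section 10.2 defines the procedure-related category as "An Adverse Event that is directly related to the insertion or surgical modification of the system". A note to that row generally leaves out events inherent to any surgery and indirect consequences of the procedure. The system-related row covers events arising from a component: device, RAMware, programmer, insertion tool or Holter. Table 7 in Section 10.3.1 gives investigators and sponsor the same choices plus Procedure, and nothing else.

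The study specifies procedures beyond insertion. Section 8.5.3 states, for each RHC, "At the conclusion of the recovery period, the posture test will be performed". Section 8.5.8 describes that test as "four different postures: standing, supine on back, lying down on left side and lying down on right side". Section 8.5.7 has a limited version at insertion, standing and supine. Section 8.5.3 also asks for cardiac output and blood pressure "at least every 2 minutes during the drug or exercise challenge and recovery". The six-minute hall walk is optional (Table 3 and Section 8.5.4).

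**The concern.** The posture test calibrates the accelerometer readings and is not part of the subject's care. It asks subjects with heart failure or exertional dyspnea to stand, in one setting directly after RHC recovery. If a subject falls and is injured, the event does not result from a system component and is not related to insertion or surgical modification. On the plain text the site has no duty to complete an AE form unless the subject dies, even if the injury is serious.

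Under Section 11 there is no independent AE committee and no data monitoring committee; sponsor personnel review the AEs. That review depends on what sites are required to submit. Harm from the study's own procedures could then go without a seriousness and relatedness assessment, and the final AE tables could understate what participation involves.

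**Working it through.** The plan has no figure to reproduce. The check is a reading of the rule against an example, followed by a count of exposure.

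**Test case: non-fatal fracture from a fall while standing in the posture test**

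| Question | Source | Answer |
|---|---|---|
| Is it an AE? | Table 6, AE definition | Yes |
| Did it result from a system component? | Table 6, system-related row | No, unless the programmer, RAMware or Holter caused it |
| Is it directly related to insertion or surgical modification? | Table 6, procedure-related row | No |
| Is it a serious event leading to death? | Section 10.1 | No |
| Must it be collected as an AE? | Section 10.1 | No |
| Is there a relatedness option that fits? | Table 7 | No |

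**Does other wording change the answer?**

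- The general AE definition carries "NOTE 2: This definition includes events related to the procedures involved". This says what an AE is, not which AEs are collected.
- The causal-relationship row begins "The event is associated with the device or study procedures beyond reasonable doubt when". It is wider than the procedure-related row, but it grades an event once reported.
- Section 9.1 says health is assessed for any AEs at office visits, and Section 8.6 refers to relevant AEs without defining the term there. Neither overrides Section 10.1.
- Section 8.5.6 collects cardiovascular-related health care utilizations. Syncope leading to care could be recorded there; an emergency visit for a fracture would not qualify on its face. The AE form, not the utilization form, is where Section 10.1 asks for seriousness and relatedness.

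**Exposure ceilings**

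Inputs: up to 30 subjects and up to 3 RHCs each (Section 5); two scheduled visits, at 6 and 12 months (Section 8.5.4); one insertion.

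- Posture tests at RHC: 30 × 3 = 90.
- Posture tests at visits: 30 × 2 = 60 if every subject has them. Section 8.5.8 limits them to subjects with an implanted pulmonary artery pressure sensor. Table 3 and Section 8.5.4 list them without that limit. The number of sensor subjects is not given, so the ceiling lies between 0 and 60.
- Limited posture tests at insertion: 30 × 1 = 30.

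The RHC and visit ceilings are unlikely to be reached together. A visit may be forgone if an RHC falls in its window, subjects may exit after three RHCs, and RHCs are done only when clinically indicated. No event rate is given, so no expected number of events can be calculated.

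**The case against.** The strongest reply is that selective AE collection is a deliberate and reasonable choice for an observational feasibility study with no safety endpoints, and that much is captured anyway. Events from the Holter, programmer or RAMware are system-related and collected. Where relatedness to the device cannot be assessed, Table 6 classes the event as possible rather than excluding it. Under Section 8.6 the sponsor's safety representative reviews health care utilizations as well as AEs. Investigators must also follow local and review-board reporting rules (Section 10.3.2). The RHC itself is clinically indicated and follows institutional practice, so an access-site bleed ordinarily belongs to clinical care. No specific harm from more frequent pressure or output readings has been identified.

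Most of this stands, and it rules out several stronger readings that a reader might infer:

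- That the sponsor cannot see any harm from these procedures. Sections 8.5.6 and 8.6 show that some cardiovascular events would reach the safety reviewer.
- That whole RHC sessions or visits fall outside AE collection. System-related AEs are collected at all of them.
- That the study lengthens RHC recovery. Sections 5.2 and 8.5.3 say only that the Holter keeps recording during it.
- That the hall walk is required. It is optional.

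The reply does not cover a non-fatal, non-cardiovascular injury that no component caused. Selective collection would be a sufficient defense if the plan said it meant to exclude such events. Instead its wording on procedures points both ways.

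**Conclusion.** The concern holds in a limited form. Read together, Sections 10.1 and 10.2 and Table 7 do not require AE reporting of a non-fatal event caused by a study procedure other than insertion or surgical modification, unless a system component caused it. This follows from the stated rule, so it is more than a missing detail, and it conflicts with the wider procedure wording elsewhere in Table 6.

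The affected exposure is at most 90 posture tests at RHC and 30 at insertion, plus between 0 and 60 at visits depending on how many subjects carry a pressure sensor. Optional hall walks and the added RHC measurements share the gap. The number of events missed is unknown and may be small.

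The conclusion assumes that sites apply the definitions literally. The procedure handbook and the draft case report forms are under separate cover and could contain instructions not visible here. The change is worth making; the gap does not threaten the primary objective.

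**What to change.** 1. In Table 6, extend the procedure-related row with wording such as: *or to any procedure performed solely for this study, including posture tests, the optional hall walk when done, and study-specified measurements added to the clinically indicated RHC*.
2. Add a matching relatedness option for investigator and sponsor in Table 7 and on the AE form.
3. Align Section 10.1, the AE definition and causal-relationship rows of Table 6, and Table 7, so that procedure has one meaning throughout.

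Holter application needs no new category because Holter is already a relatedness option, though the Holter row in Table 6 describes the implant tool and should be corrected in the same edit. The new wording should not mention added recovery time.

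The cost is an edit to two tables and one section, one case report form option and a small number of extra AE forms. No procedure, visit or staff is added.

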6.6. Product Use

The Reveal LINQ™ device is a programmable cardiac monitor that continuously monitors a patient's ECG and other physiological parameters.

It will be implanted in all the subjects enrolled in the study and the device implant procedure will be performed as per routine practice according to the Clinician Manual. After implant, the investigational software will be downloaded onto the device making it interventional. In order to complete this installation, an ad-hoc 2090 Programmer, with the investigational software on it will have to be provided to the site before study start.

The subject will be provided of:

- A Patient Assistant that will allow him/her to record (mark) heart rhythm in case he/she experiences any specific symptoms that could be related to his/her cardiac condition, such as but not limited to fainting, palpitations, dizziness, and shortness of breath.
- A Carelink Monitor that will allow him/her to perform automatic daily transmissions and manual transmissions once a month.

At every follow-up visit, a device interrogation will be performed in order to download on a USB flash drive information recorded by the device on subcutaneous impedance values and standard LINQ™ information such as ECGs and Trends (Cardiac Compass, Histograms, and Longest AF).

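### The default exclusion in the Procedure Related definition leaves non-fatal anaesthesia complications and indirect harms of the study-required LINQ insertion without a clear required AE route, and is in tension with the Unavoidable AE rule

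*Combined protocol and SAP*

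**What the plan says.** Section 10.1 sets the scope of collection: "Reveal LINQ™ system and procedure-related adverse events will be collected throughout the study duration". One class is added whatever its cause: "all serious adverse events (SAEs) leading to death should be reported, regardless of relatedness".

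Table 6 in section 10.2 defines Procedure Related as "An Adverse Event that is directly related to the insertion or surgical modification of the system". A note qualifies it: "In general, this excludes events that are inherent to any surgical procedure (e.g. anesthesia complications) as well as indirect subsequent consequences of the procedure". For the indirect class, the note's example is an analgesic reaction.

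The general adverse event definition in the same table is wider: "NOTE 2: This definition includes events related to the procedures involved".

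A second rule also deals with harms that come with surgery. Table 6 describes an Unavoidable Adverse Event as "An Adverse Event inherent to a surgical procedure that is expected to occur in all subjects for a projected duration". It lists pocket or incisional pain with a limit of 72 hours, and mild to moderate bruising with a limit of 168 hours. Section 10.1 gives the reporting consequence: "Unavoidable AEs, listed in Table 6, need not be reported unless the AE worsens or is present outside the stated timeframe post-insertion".

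On who receives the device, section 6.6 says: "It will be implanted in all the subjects enrolled in the study". None of the inclusion criteria in section 7.3 asks for a clinical indication for a LINQ.

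**The concern.** The insertion happens because of the study, so a complication of the anaesthesia or analgesia given for it is a harm of taking part, not background surgical risk. Such an event is an AE under the general definition. The collection rule, however, depends on relatedness, and the note by default takes this kind of event out of the procedure-related class.

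The note draws no line at seriousness, so a non-fatal event that leads to hospitalisation is treated like a trivial one. Section 11 provides neither an adverse event advisory committee nor a data monitoring committee, and sponsor staff review the AEs that are reported. An event that no rule requires sites to report may never reach that review. Section 8.9 likewise recommends follow-up to resolution before exit only for system- or procedure-related AEs.

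The two rules on surgery-inherent events also give different answers for the same event, so sites could handle it differently.

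**Working it through.** No arithmetic underlies this point, and the plan gives no figure to reproduce. The check follows each type of event through the rules.

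Routes into the AE data:

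1. Procedure related (section 10.1, and Table 6 with its note).
2. System related, meaning the device, RAMware, programmer, insertion tool or Holter (section 10.1 and Table 6).
3. A serious event leading to death, whatever its cause (section 10.1).

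A partial route outside the AE data is the HCU form (sections 8.5.5 and 8.5.6).

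| Event after LINQ insertion | Procedure related | System related | Fatal route | Required AE form? |
|---|---|---|---|---|
| Non-fatal anaesthesia complication | Excluded by default (named in the note) | Not ordinarily: no system component causes it | No | No clear route, even if serious |
| Non-fatal analgesic reaction | Excluded by default (named in the note) | Not ordinarily | No | No clear route, even if serious |
| Pocket infection, tissue or vascular trauma, erosion, migration | Direct result of insertion | Often also device or insertion tool | – | Yes |
| Bruising still present on day 10 | Excludable under the note as inherent to surgery | Possible if device-caused | No | Rules disagree |
| Death from any cause | – | – | Yes | Yes |

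The bruising row: day 10 is 10 × 24 = 240 hours, which is beyond the 168-hour limit. Section 10.1 and the Unavoidable AE row therefore make it reportable. The note has no time limit, so a site may class the same bruise as inherent to surgery, hence not procedure related and outside collection. Incisional pain on day 5 (5 × 24 = 120 hours, beyond 72) raises the same question. If the note already removed all surgery-inherent events, the time limits would have little work to do.

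The HCU route: section 8.5.6 restricts collection to cardiovascular utilizations. The synopsis, section 5 and section 8.5.5 first list hospitalisations and emergency visits in general terms, then add a reporting instruction for cardiovascular ones. Whether a non-cardiovascular admission is captured is therefore unclear. In either case it would be on an HCU form, not recorded as an AE with relatedness and seriousness assessed.

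Section 10.3.1 asks sites to contact the study team urgently about an SAE, and section 10.3.2 holds investigators to local and IRB reporting duties. Neither adds these events to the list in section 10.1.

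**The case against.** The strongest reply is that the note states a general default, not an absolute bar. Investigator and sponsor both classify relatedness (Table 7), so a serious anaesthesia event could still be judged procedure related and reported. This stands, and it means one cannot say that no such event would be recorded. It does not close the gap: reporting would rest on discretion, and discretion is what lets sites differ.

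Secondly, the two rules can be read together. The note guides relatedness. The Unavoidable AE rule governs reporting of a narrower class, and a specific timed rule can be taken to override a general note. That is a reasonable reading, so this is a tension more than a flat contradiction. But the plan does not say which prevails, and the two rules sit in different places: definition and limits in Table 6, reporting consequence in section 10.1.

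Thirdly, this is an unpowered feasibility study with no safety endpoint (section 8.6), and section 11 says it will not supply safety data. That limits what is at stake, but the protocol still undertakes to collect and review AEs of the insertion.

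A reader might infer that harms of the insertion in general go uncollected, pocket infection and tissue trauma included. The documents do not support that. Those events are direct results of the insertion, or arise from the device or insertion tool, and remain in scope.

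A reader might also infer that the risk statements in sections 9.1 and 9.3 are understated as a result. They are not built on any AE tally from this study. They are prospective statements about the device and the RAMware, so the note cannot bias them.

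**Conclusion.** The point holds in a limited form. For two classes of event, those inherent to surgery in general and those that follow indirectly from the procedure, the plan by default leaves non-fatal cases without a clear required AE route, serious ones included. It also leaves open how the note relates to the 72- and 168-hour limits.

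This rests on reading section 10.1 as the complete list of collected AEs, and on the insertion being required by the study, as sections 6.6 and 7.3 indicate. The documents give no rate for such events, so no expected count is offered. The exposed group is at most 30 subjects.

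The consequence is incomplete, and possibly site-dependent, safety reporting. The impedance–haemodynamic characterisation is unaffected. The change is worth making because it is cheap.

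**What to change.** Amend the Procedure Related row of Table 6 so that AEs caused by the LINQ insertion or a system modification are collected whether direct or indirect, including those from anaesthesia and analgesia. At a minimum, collect all that meet the SAE definition. State that the Unavoidable AE rule, with its time limits, is the only exemption, and align section 10.1 with this. Add a direct/indirect flag to the AE form so that the narrower procedure-related tally can still be produced for comparison with other LINQ studies.

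The cost is a wording change, one extra field and a few more AE forms. The procedure-related AE count may look slightly less favourable.
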